5.3 Exploratory Endpoints

The exploratory endpoints are:

- Mean change on the Menopause-Specific Quality of Life (MENQOL) Total Score from baseline to specified time points (week 4, 12, 24 and 52).
- Mean change on the MENQOL Domain Scores from baseline to specified time points (week 4, 12, 24 and 52).
- Mean change on the Euro-Qol 5D-5L (EQ-5D-5L) Visual Analog Scale (VAS) from baseline to specified time points (week 4, 12, 24 and 52).

- Euro-Qol 5D-5L (EQ-5D-5L) domain scores at specified time points (week 4, 12, 24 and 52).
- Change from baseline to specified time points in serum concentrations of sex hormones and sex hormone-binding globulin (SHBG) (week 4, 12, 24, 52 and 55).
- Plasma concentration of fezolinetant and the fezolinetant metabolite ESN259564 at specified timepoints (week 4, 12, 24 and 52).

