6.5 Analysis of Safety

Overall long-term safety of fezolinetant and the effect of fezolinetant on endometrial health will be the primary objective of this study. The safety assessments include adverse events, laboratory assessments, vital signs, C-SSRS, ECG, endometrial health assessment and imaging (mammogram, DXA, TVU). In all analysis of safety, the treatment group includes placebo, fezolinetant 30mg, fezolinetant 45mg and fezolinetant total will be presented by treatment group for SAF, unless specified otherwise. For analyses by visit, the analysis windows from Section 6.10.1 will be applied. Except for adverse events and follow-up visit data, only data up to one day after the last dose date will be considered for the analyses.

The baseline value for safety endpoint will be the last non-missing value taken on or prior to first dose of study drug unless otherwise noted.

Primary Safety Variables

- Frequency and severity of AEs.
- Percentage of subjects with endometrial hyperplasia.
- Percentage of subjects with endometrial cancer.

Secondary Safety Variables

- Change from baseline in endometrial thickness at 12 months.
- Percentage of subjects with disordered proliferative endometrium.
- Change from baseline in bone mass density (BMD) and trabecular bone score (TBS) at hip and spine at 12 months.
- Change from baseline to each timepoint in vital signs: sitting systolic and diastolic blood pressure and pulse rate.

- Change from baseline to each timepoint in laboratory tests: hematology, biochemistry and urinalysis.
- C-SSRS at each timepoint.
- Change from baseline to each timepoint in ECG parameters

Exploratory Safety Variables

- Change from baseline to specified time points in serum concentrations of sex hormones and sex hormone-binding globulin (SHBG) (week 4, 12, 24, 52 and 55).
- Plasma concentration of fezolinetant and the fezolinetant metabolite ESN259564 at specified timepoints (week 4, 12, 24 and 52).

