6.5.2 Clinical Laboratory Evaluation

Quantitative values evaluated by the central laboratory including hematology, biochemistry, and urinalysis will be summarized using mean, standard deviation, minimum, maximum and median by treatment group at each analysis visit. Additionally, a within-subject change will be calculated as the post-baseline measurement minus the baseline measurement and summarized in the same way. Each laboratory result will be classified as low (L), normal (N), or high (H) at each visit according to the laboratory supplied reference ranges.

Frequency tabulations of qualitative clinical laboratory variables (urinalysis) will be presented for each treatment group at each visit.

Number and percentage of subjects with platelets $< 150 \times 10^{9}$ /L will be separarely summarized for each treatment group.

For hematology and biochemistry shift tables will be presented for each treatment group:

Summary shifts of reference range changes from baseline to worst finding during the treatment period (shift from normal or high to low, shift from normal or low to high, categorized increase [shift from low to normal or from normal to high], categorized no change [value stays in the same reference range], categorized decrease [shift from high to normal or from normal to low]).

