6.5.2.1 Liver Safety Assessment

The liver safety assessments will be summarized by the categories below based on the measurements from Alkaline Phosphatase (ALP), Alanine Transaminase (ALT), total

bilirubin, Aspartate Transaminase (AST) and their combination. These parameters will be based on measurements from a central laboratory.

The subject's highest value during the investigational period (from day of first dose of study drug until last dose of treatment period + 1 day) will be used.

- ALT > 3xULN, > 5xULN, > 8xULN, > 10xULN, >20xULN
- AST > 3xULN, > 5xULN, > 8xULN, > 10xULN, > 20xULN
- ALT or AST > 3xULN, > 5xULN, > 8xULN, > 10xULN, >20xULN
- ALP > 1.5 xULN
- Total Bilirubin >2xULN
- (ALT or AST > 3xULN) and Total Bilirubin > 2xULN
- (ALT or AST > $3 \times ULN$) and Total Bilirubin > $1.5 \times ULN$
- (ALT or AST > 3xULN) and ALP< 2xULN and Total Bilirubin > 2xULN

The last 2 criteria where 2 or more parameters are evaluated will be with the measurements on the same day or up to 1 day apart. The denominator for each criterion will be the number of subjects who have at least one value during the double-blind investigational period. The number and percentage of subjects meeting the criteria during the double-blind investigational period will be summarized by treatment group.

Due to COVID-19, patients might not be able to visit the clinical site and have clinical laboratory tests taken at the clinical site and evaluated by the central laboratory, in this case clinical laboratory tests can be taken by a local laboratory. The liver biochemistry safety assessments will be summarized including central and locally collected laboratory data due to COVID-19. This analysis is considered the primary analysis for the liver safety assessments.

The secondary analysis for liver biochemistry will be repeated by the data evaluated by the central laboratory but excluding the data that are impacted by COVID-19, which include the data recorded after the subjects were diagnosed of COVID-19, after study drug discontinuation due to COVID-19, during dose interruption due to COVID-19, and visits that are out of protocol window or data collected via home visits due to COVID-19 recorded in the eCRF.

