6.10 Additional Conventions

6.10.1 Analysis Windows

Study Day for analysis windows will be calculated as date of visit/assessment – first dose date +1.

Study Day for the follow-up (FUD) phase will be calculated as date of visit/assessment – last dose date of study treatment (Date of EOT).

Except for adverse events, for the analysis window (weeks prior to the follow-up period), the last day is always 1 day after the last day of exposure to double-blind treatment.

The end of overall treatment is defined as the last day of treatment +1 and the follow-up period begins at last overall treatment + 2 days and onward (Follow-up Study Day 2).

The data summary by visits will be done following the analysis windows specified in the table below:

Analysis	Scheduled	Analysis Windows (day)				
Visits	Day in Protocol	a)	b)	c)	d)	e)
Baseline	Day 1	Last non-missin	ng value on or prio	or to day 1 (inclu	sive)	
Week 2	Day 15	2 to 22				
Week 4	Day 29	23 to 43	2 to 43	2 to 57		
Week 8	Day 57	44 to 71	44 to 71			
Week 12	Day 85	72 to 99	72 to 99	58 to 127	2 to 127	
Week 16	Day 113	100 to 127	100 to 127			
Week 20	Day 141	128 to 155	128 to 155			
Week 24	Day 169	156 to 183	156 to 183	128 to 267	128 to 267	
Week 28	Day 197	184 to 211	184 to 211			
Week 32	Day 225	212 to 239	212 to 239			
Week 36	Day 253	240 to 267	240 to 267			
Week 40	Day 281	268 to 295	268 to 295			
Week 44	Day 309	296 to 323	296 to 323			
Week 48	Day 337	324 to 351	324 to 351			
Week 52	Day 365	352 to 376	352 to 376	268 to 376	268 to 376	2 to 376
Follow-up	Day 386	Last treatment + 2 days and onwards				

a) Apply to Clinical laboratory and urinalysis

b) Apply to Vital signs

- c) Apply to Blood PD/PK sample, EQ-5D-5L, MENQoL
- d) Apply to C-SSRS
- e) Apply to 12-lead ECG

For TVU and DXA, the week 52 analysis window is day 2 to last treatment + 30 days. For endometrial biopsy, refer to Section 6.5.5 for analysis window.

As a general rule, if more than one observation exists within the analysis window, the observation closest to the scheduled visit day will be selected for that visit. If there are two observations that have the same distance from the scheduled day, the value that is after the scheduled day will be selected in the analysis. If more than one observation is made on the same day, an average value if continuous or the worst value if categorical will be included in the analysis.

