The Follow Up visit (Week 55) will include all data collected beyond 1 day after the last dose of the study drug. If there are more than one value, then the value that is closest to Day 386 from the last dose of study drug will be selected for the analysis. The same logic will be applied as in above for more than one value.

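### SAP 6.10.1 chooses among repeat follow-up values by nearness to day 386 after last dose, but Day 386 counts from first dose, so a retest can displace the Week 55 value in descriptive Follow-up rows

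*SAP*

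**What the plan says.** SAP 6.10.1 sets up two clocks. Study Day counts from first dose, with first dose as Day 1. For follow-up, "Study Day for the follow-up (FUD) phase will be calculated as date of visit/assessment – last dose date of study treatment", so the last dose date is follow-up day (FUD) 0.

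The window table in the same section gives the Follow-up visit a scheduled day of 386 and the window "Last treatment + 2 days and onwards", with no upper limit. If several values fall in it, "the value that is closest to Day 386 from the last dose of study drug will be selected for the analysis". The tie convention for the other visits carries over: at equal distance, "the value that is after the scheduled day will be selected in the analysis".

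The protocol places Visit 16 about three weeks after last dose, for completers and for women who stop early (Table 1 footnote b; 2.2.1). Visit 15 is scheduled for Day 365 with a window of −14/+6 days (Table 1), and the last dose is taken the day before it (footnote s).

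Two passages govern where the selected value is used. SAP 6.5 states: "Except for adverse events and follow-up visit data, only data up to one day after the last dose date will be considered". SAP 5.3 names Week 55 as a time point for the hormone endpoint: "sex hormone-binding globulin (SHBG) (week 4, 12, 24, 52 and 55".

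**The concern.** A first-dose day number has been attached to the last-dose clock. No study visit falls 386 days after last dose, so a programmer must either apply the sentence literally or guess what was meant. Different guesses give different tables.

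The rule matters only when a woman has a second post-treatment value, and the protocol foresees that for laboratory tests. Protocol 5.4.3 allows abnormal results to be repeated. Protocol 12.5 has liver tests monitored every 2 to 4 weeks once drug is stopped after a liver signal. Some of those women are early discontinuers because of the liver stopping rules in Protocol 6.1, so early stopping and serial retesting tend to coincide.

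Under SAP 6.5, post-treatment laboratory values reach a summary table only through the Follow-up row. Protocol 2.2.2 describes a phase 2b subject whose transaminases were normal throughout the study and raised at the follow-up visit three weeks after last dose. In such a case the row labelled Week 55 could show a later retest. Because Protocol 5.8.6 follows adverse events until they resolve, lose clinical significance or become chronic, a later value tends to describe the end of that follow-up and not the three-week state.

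**Working it through.** **Origin of Day 386.** With first dose as Day 1, Week 55 is 55 × 7 + 1 = 386 and Week 52 is 52 × 7 + 1 = 365. This reproduces the scheduled days in the SAP table. The difference is 21 days.

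**Notation.** L is the Study Day of last dose, so Study Day = L + FUD. The Week 55 value is taken to lie on FUD 21. Ties go to the value after the target day.

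**Literal reading (target FUD 386).** The Week 55 value is |21 − 386| = 365 days from target. A later value on FUD x is selected if x ≤ 386 + 365 = 751. Any retest from FUD 22 to 751 therefore displaces it.

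**Study Day 386 reading (target FUD 386 − L).** For L < 365 the Week 55 value is 365 − L days short of target. A later value is selected if x ≤ (386 − L) + (365 − L) = 751 − 2L.

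- L = 84: up to FUD 583.
- L = 300: up to FUD 151.
- L = 350 (Visit 15 on Day 351, the earliest allowed): up to FUD 51.
- L = 364 (nominal completer): up to FUD 23, so only a retest on FUD 22 or 23.
- L = 370 (Visit 15 on Day 371, the latest allowed): the target is FUD 16 and the Week 55 value is 5 days away. No later value displaces it, but an earlier value on FUD 12 to 20 does. A value on FUD 11 ties, and the later value is kept.

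**Illustration, assuming tests on FUD 21, 28 and 56.**

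| Target | Distances | Selected |
|---|---|---|
| Literal, FUD 386 | 365, 358, 330 | FUD 56 |
| Study Day 386, L = 84 (FUD 302) | 281, 274, 246 | FUD 56 |
| Study Day 386, L = 350 (FUD 36) | 15, 8, 20 | FUD 28 |
| Study Day 386, L = 364 (FUD 22) | 1, 6, 34 | FUD 21 |
| FUD 21 | 0, 7, 35 | FUD 21 |

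**The selected value is not always the latest.** For L = 300 the target is FUD 86. Tests on FUD 21, 80 and 140 lie 65, 6 and 54 days away, so FUD 80 is selected.

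**A target of FUD 21 alone is not quite enough.** An early discontinuation (ED) visit more than 1 day after last dose also falls in the Follow-up window. Protocol 2.2.1 lets Visit 16 be timed three weeks from ED. With ED on FUD d and Visit 16 on FUD d + 21, the distances from FUD 21 are |d − 21| and d. The ED value is nearer once d ≥ 11 (at d = 11: 10 against 11).

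**Outputs not reached.** The shift tables are "Summary shifts of reference range changes from baseline to worst finding during the treatment period". The liver-category tables use the highest value "from day of first dose of study drug until last dose of treatment period + 1 day". Both stop before the follow-up period. Biopsy, transvaginal ultrasound and DXA have their own windows in SAP 6.5.5 and 6.10.1.

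**The case against.** The strongest reply is that this is a drafting slip with little reach. The table lists Day 386 as the scheduled day, so a sensible programmer would use Study Day 386, and for completers on the nominal schedule that works. Only descriptive rows depend on it. SAP 6.5.2 summarises values evaluated by the central laboratory, and the documents do not say whether retests after Visit 16 go there. The repeat provisions concern laboratory tests; nothing shows later repeats of vital signs or C-SSRS. Days 751 and 583 are formal limits, not expected retest times. Read literally, the current rule also handles a late ED visit correctly, because it takes the later Visit 16 value, whereas a bare day-21 target might not.

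All of this stands, and it sets the severity and shapes the fix. It does not rescue the sentence. The charitable reading contradicts the words that tie the day to last dose, and it still fails for early discontinuers and for completers away from the nominal schedule.

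A reader might infer three stronger things:

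- **That the rule always takes the latest value.** On the Study Day 386 reading it takes the value nearest that day, which is often but not always the latest.
- **That a liver signal would be lost from the report.** The liver-category tables never used follow-up data, and Protocol 7.6.2 keeps laboratory data in listings.
- **That adverse event counts shift.** SAP 6.5.1 gives treatment-emergent events their own end, 21 days after last dose, and this rule does not enter it.

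**Conclusion.** SAP 6.10.1 is wrong as written, with minor severity. On the literal reading, any realistic later retest displaces the Week 55 value. On the Study Day 386 reading, displacement is confined to early discontinuers and to completers off the nominal schedule, apart from a two-day margin at L = 364.

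The affected outputs are the by-visit Follow-up rows, mainly central-laboratory values. Any other Follow-up row is affected where a second post-treatment value exists, for example hormones at Week 55 or values from an ED visit more than 1 day after last dose. No primary endpoint changes.

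The arithmetic assumes that Visit 16 falls on FUD 21, as Table 1 footnote b implies. If a site kept the Day 386 date after an early Visit 15 (L = 350), Visit 16 would fall on FUD 386 − 350 = 36. The Study Day 386 reading would then select it, while the literal reading would still prefer a later retest.

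The number of women affected cannot be computed, because the documents give no rate of repeat testing after treatment.

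**What to change.** In SAP 6.10.1, replace the selection sentence with: *the Visit 16 value will be selected where there is one; otherwise the value closest to Follow-up Study Day 21 (3 weeks after last dose) will be selected.*

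The first clause stops retests and late ED values from displacing Visit 16, whatever its exact date. The second gives women without a Visit 16 value a target on the correct clock. The existing rules for ties and for several values on one day can stay.

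The cost is one sentence and the matching line in the programming specification, with no new data and no change to any primary analysis. If the SAP is already final, the rule actually used can be recorded in the clinical study report, as SAP section 1 provides.

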6.10.2 Imputation Rules for Incomplete Dates

In case of missing partial start and stop dates for concomitant medications or targeted medical history, the following rules will be used:

If the start date is missing or partial:

- if the month is missing, use January
- if the day is missing, use the first day of the month under consideration
- if the year is missing, use year of the informed consent date
- if the entire date is missing, use informed consent date

If the stop date is missing or partial:

- if the month is missing, use December
- if the day is missing, use the last day of the month under consideration
- if the year or the entire date is missing, set the stop date to December 31st, 2099

If the imputed start date is after the stop date, then the imputed start date will be 1 day prior to the stop date.

For AEs, a missing or incomplete onset date will be imputed according to the following conventions.

If an onset date is missing, the imputed onset date will be the date of first dose of study drug.

If only the year is known for the AE onset date, the imputed onset date will be the latest of the following non-missing dates:

- Date of first dose of study drug
- January 1 of the year of AE onset date

If only the month and year is known for the onset date, set the surrogate onset date to the first day of that month and then apply the following rules.

- If the month and year of the onset date is prior to the month and year of the first dose of study drug, then the surrogate onset date will be the imputed onset date.
- If the month and year of the onset date is on or after the month and year of the first dose of study drug, then the imputed onset date will be the latest of the following non-missing dates:
 - Date of first dose of study drug
 - Surrogate onset date

If the imputed onset date is after the adverse event end date, the imputed onset date will be the same as the adverse event end date.

7 **REVISION AND RATIONALE**

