2.2 Study Design and Dose Rationale

2.2.1 Study Design

This is a 52-week randomized, placebo-controlled, double-blind, parallel-group, multicenter clinical study to assess the safety and tolerability of fezolinetant in women seeking treatment for VMS associated with menopause. The study visits will be performed on an outpatient basis.

This study will consist of a screening period (days -35 to -1, including the screening visit [visit 1] assessments), a 52 week treatment period (day 1 [visit 2] to week 52 [visit 15]) and a follow up visit (week 55 [visit 16]) 3 weeks after the last dose of study drug. An extra 15 screening days are allowed for repeat biopsy, if necessary (days -50 to -1, including the screening visit [visit 1] assessments).

The screening visit (visit 1) will occur up to 35 days prior to treatment initiation. Eligibility will be assessed via physical examination, clinical laboratory testing, urine pregnancy test, vital signs, ECG, Papanicolaou (Pap) test (or equivalent cervical cytology), mammography,

transvaginal ultrasound (TVU) and endometrial biopsy. To participate in the study, subjects must be seeking medical treatment for relief of VMS.

Subjects may be retested for assessments up to 1 time upon approval of the medical monitor within the current 35-day screening window and will retain the same subject screening identification number.

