5.8 Adverse Events and Other Safety Aspects

5.8.1 Definition of Adverse Events

An AE is any untoward medical occurrence in a subject administered a study drug, and which does not necessarily have to have a causal relationship with this treatment. An AE can therefore be any unfavorable and unintended sign (including an abnormal laboratory finding), symptom, or disease (new or exacerbated) temporally associated with the use of a medicinal product whether or not considered related to the medicinal product.

In order to identify any events that may be associated with study procedures and could lead to a change in the conduct of the study, Astellas collects AEs even if the subject has not received study drug treatment. AE collection begins after the signing of the informed consent and will be collected until 21 days after the last dose of study drug or the subject is determined to be a screen failure.

Care will be taken not to introduce bias when detecting AEs and/or SAEs. Open-ended and non-leading verbal questioning of the subject is the preferred method to inquire about AE occurrences.

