7.11 Additional Conventions

The start and stop dates of AEs and concomitant medication will be imputed. The imputed dates will be used to allocate the concomitant medication and AEs to a treatment group, in addition to determining whether an AE is/is not treatment emergent. Listings of the AEs and concomitant medications will present the actual partial dates; imputed dates will not be shown. See the SAP for details of the definition for analysis windows to be used for analyses by visit.

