6.5.1 Adverse Events

Per protocol, a treatment emergent adverse event (TEAE) is defined as the AEs that occurred on or after first dose of study drug and 21 days after the last dose of study drug (when AE collection closes).

A study drug-related TEAE is defined as any TEAE with a causal relationship of YES by the investigator.

The sponsor has a list of events that they classify as "always serious" events. If an AE is reported that is considered by the sponsor to be an SAE per this classification as "always serious", the AE will be treated as an SAE in tables and listings, and flagged as 'always serious' in AE listings.

An overview table will include the following

- Number of TEAEs,
- Number and percentage of subjects with TEAEs,
- Number of drug related TEAEs,
- Number and percentage of subjects with causally drug related TEAEs,
- Number of serious TEAEs,

- Number and percentage of subjects with serious TEAEs,
- Number of serious drug related TEAEs,
- Number and percentage of subjects with serious drug related TEAEs,
- Number of TEAEs leading to permanent discontinuation of study drug,
- Number and percentage of subjects with TEAEs leading to permanent discontinuation of study drug, and
- Number of deaths.

In order to adjust for differences in subjects' durations and the potential differential dropout rates between the treatment groups, an overview table to report exposure adjusted incidence rate (per 100 subject-years) for the above AE categories will be summarized. The total subject-years of exposure is calculated as the sum over subjects of the total duration of exposure divided by 365.25:

$$\sum_{i} \frac{ld_i - fd_i + 1}{365.25},$$

where fd_i and ld_i denote the first dose date of study drug and the last dose date of study drug for subject *i*.

The number and percentage of subjects with TEAEs in the following AE categories will be summarized for each treatment group by system organ class (SOC), high level term (HLT) and preferred term (PT):

- TEAEs
- drug related TEAEs.

The number and percentage of subjects with TEAEs in the following AE categories will be summarized by SOC and PT:

- serious TEAEs,
- drug related serious TEAEs,
- TEAEs leading to permanent discontinuation of study drug,
- drug related TEAEs leading to permanent discontinuation of study drug,
- TEAEs that equal to or exceed a threshold of 5.0% in any treatment group (threshold is based on PT).

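### A year-only AE onset in the year before first dose is imputed to the first-dose date, so the event counts as treatment-emergent unless an end date before dosing is recorded

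*SAP*

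**What the plan says.** SAP 6.10.2 gives separate AE onset rules for each degree of missing information.

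- Whole date missing: use the first-dose date.
- Year only: "If only the year is known for the AE onset date, the imputed onset date will be the latest of the following non-missing dates". The candidates are the first-dose date and "January 1 of the year of AE onset date". There is no separate step for an onset year before the year of first dose.
- Month and year: a surrogate onset is set to the first of the month. "If the month and year of the onset date is prior to the month and year of the first dose of study drug", that surrogate date stands; otherwise the later of first dose and the surrogate is used.
- End-date cap, applied last: "If the imputed onset date is after the adverse event end date, the imputed onset date will be the same as" the end date.

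Imputed dates have consequences. Protocol 7.11 uses them to allocate events to treatment "in addition to determining whether an AE is/is not treatment emergent". SAP 6.5.1 has TEAEs "defined as the AEs that occurred on or after first dose of study drug and 21 days after the last dose of study drug", so an onset on the first-dose date itself qualifies.

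Events before dosing are in the database, because under Protocol 5.8.1 "AE collection begins after the signing of the informed consent".

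**The concern.** Counting an AE as treatment-emergent when its timing is unknown is a normal cautious default, and the rule for a wholly missing date does that. The year-only rule goes further. If the recorded year is earlier than the year of first dose, the timing relative to treatment is known, and the rule replaces that year with a different one.

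The section is also inconsistent with itself. The same event is pre-treatment if recorded as December 2019 but can become treatment-emergent if recorded as 2019. Losing the month should not turn a known pre-treatment event into an on-treatment one.

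TEAE status determines which events enter the TEAE overview, the serious, drug-related and discontinuation tables, and the exposure-adjusted rates. AESIs are defined among TEAEs (SAP 6.5.1) and are reported with rates, odds ratios and exact intervals (SAP 6.5). These tables summarise the primary endpoint of AE frequency and severity. For rare events a single record can show: at the 0.10% background rate in the SAP section 3 table, an arm of 580 expects 580 × 0.001 = 0.58 events.

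**Working it through.** The plan states no figure for this point, so the check applies its date rules to test cases.

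**Rules as formulas.** Let F be the first-dose date, Y the recorded onset year and E the AE end date.

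1. Year-only imputation: D = later of F and 1 January of Y.
2. Cap: if D is after E, set D = E.
3. An onset D on or after F meets the start condition for a TEAE.

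If Y is before the year of F, 1 January of Y is always before F, so step 1 always gives D = F. Only step 2 can then move the onset before F, and it does so only when E is before F.

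**Test cases.** Illustrative first dose 15 Jan 2020; the onset is recorded either as 2019 or as Dec 2019.

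| AE end date | Recorded 2019: imputed onset | TEAE? | Recorded Dec 2019: imputed onset | TEAE? |
|---|---|---|---|---|
| Ongoing or missing | 15 Jan 2020 | Yes | 1 Dec 2019 | No |
| 1 Feb 2020 | 15 Jan 2020 | Yes | 1 Dec 2019 | No |
| 15 Jan 2020 (first dose) | 15 Jan 2020 | Yes | 1 Dec 2019 | No |
| 5 Jan 2020 | 5 Jan 2020 (cap) | No | 1 Dec 2019 | No |
| 28 Dec 2019 | 28 Dec 2019 (cap) | No | 1 Dec 2019 | No |

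Partial end dates are a further gap. Protocol 7.11 says AE stop dates will be imputed, but the stop-date rules in SAP 6.10.2 cover only concomitant medications and targeted medical history. For an AE with a partial end date, the cap is therefore undefined.

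**Can it occur?** Under Protocol 2.2.1, "The screening visit (visit 1) will occur up to 35 days prior to treatment initiation", with 15 extra days allowed for a repeat biopsy. The planned study period in the Synopsis, 2Q2019 to 3Q2022, contains several year-ends.

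**How many women could be exposed?** Assume first doses spread evenly over a 365-day year and every woman using her full window. A woman then has at least one screening day in the previous year if she is first dosed in the first 35 (or 50) days of the year:

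- 35-day window: 35/365 = 9.6% of women.
- 50-day window for everyone: 50/365 = 13.7% of women.

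The share of all screening days that fall in the previous year is about half of this:

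- (1 + 2 + … + 35)/(35 × 365) = 630/12,775 = 4.9%.
- (1 + 2 + … + 50)/(50 × 365) = 1,275/18,250 = 7.0%.

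An affected record needs, in addition, an AE starting on those days, an onset known only to the year, and no end date before first dose. The documents give no rate for that combination.

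**With a guard added.** Keeping 1 January of the onset year when Y precedes the year of F gives 1 Jan 2019 in all five cases, and none is a TEAE. Same-year and later-year onsets are unchanged (15 Jan 2020 for 2020 and 1 Jan 2021 for 2021).

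**The case against.** The strongest reply is that the affected set may be close to empty. An AE must begin after consent, and screening lasts at most 35 days, or 50 with a repeat biopsy. A prior-year onset is therefore confined to roughly the last seven weeks of that year. The site would have to know the year of a recent event but not its month, although AEs are monitored continuously and Protocol 8.1 asks for data entry within 5 days of the visit. The rule is also identical in all blinded arms, errs towards counting events, and leaves the actual partial dates visible in the listings. All of this stands and limits the point to a small correction. It does not make the rule right, because the rule still overrides a recorded year.

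A reader might infer four stronger things that the documents do not support:

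- That every year-only, prior-year event becomes a TEAE. The cap keeps events with an end date before first dose out.
- That 10% to 14% of women or events are misclassified. Those figures are ceilings on women with any prior-year screening day. The upper one requires everyone to use an extension reserved for repeat biopsy.
- That the comparison between arms is biased. Nothing in the rule depends on arm.
- That the primary endpoints are directly redefined. The listed AE endpoint is frequency and severity of AEs, and TEAE status is the way it is summarised. The hyperplasia and cancer endpoints rest on biopsy diagnoses (SAP 6.5.5), not on AE onset dates.

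**Conclusion.** The year-only rule is wrong as written for one case: a recorded onset year before the year of first dose, in an event that is ongoing, ends on or after first dose, or has no usable end date. In that case the misclassification is certain, because it follows from the date logic alone.

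The size is likely very small. At most 9.6% of women could have any prior-year screening days, or 13.7% if all used the extension, and only a fraction of those would have a qualifying record. Both ceilings assume even accrual and full use of the window. The recruitment pause described in SAP Appendix 1 makes even accrual doubtful, and first doses clustered just after a year-end would raise the share. No direction between arms is claimed. The reason to act is that a stated rule contradicts recorded data in the tables summarising a primary endpoint, and the remedy costs almost nothing.

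**What to change.** Give the year-only rule in SAP 6.10.2 the guard that the month-and-year rule already has. If the onset year is before the year of first dose, impute a date in the onset year, so that the event is not treatment-emergent. Otherwise use the later of first dose and 1 January of the onset year, as now.

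The date may be 1 January, which matches the earliest-date convention of the month-and-year rule, or 31 December; TEAE status is the same. No informed-consent floor is needed: an AE that starts after consent in a given year always has 31 December of that year on or after consent, and with 1 January the status does not change.

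The cost is one sentence and one line of code, with no new data. SAP section 1 has the final version approved before database lock and unblinding, which is when to make the change.
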